***Proposed Dose and Schedule for Phase 2 Clinical Trials***

Starting doses in multiple-dose studies were 25, 50, 75, and 100 mg administered orally once daily with the majority of patients receiving the 50-mg dose. Patients in sunitinib studies have been treated on four different schedules: schedules 4/1 and 4/2 comprised 4 consecutive weeks of daily dosing followed by a 1- or 2-week rest period, respectively, while schedules 2/1 and 2/2 comprised 2 consecutive weeks of daily dosing followed by a 1- or 2-week rest period, respectively. The majority of subjects were treated on schedules 4/2 or 2/2 in phase 1 studies. Schedule 4/2 has been well tolerated with generally mild to moderate adverse effects at a 50 mg daily dose. Alternate regimens of sunitinib are being explored; 50 mg of sunitinib daily for 2 weeks followed by a 1-week off-treatment period (sunitinib 2/1) (Britten et al., 2008), while another schedule is sunitinib 37.5 mg as a CDD (George et al., 2008). Both schedules were well-tolerated, achieved therapeutic plasma concentrations and showed no significant accumulation of the drug.

## 18.2 Appendix B: Medication Diaries

CTEP-assigned Protocol # \_\_\_\_\_

### 18.2.1 AZD6244 hydrogen sulfate

#### PATIENT'S MEDICATION DIARY

Today's date \_\_\_\_\_ Agent \_\_\_\_\_ AZD6244 \_\_\_\_\_  
Patient Name \_\_\_\_\_ (initials acceptable) Patient Study  
ID \_\_\_\_\_

1. Complete one form for each cycle of treatment.
2. AZD6244 should be stored at room temperature.
3. You will take AZD6244 by mouth twice each day about 12 hours apart. Take the medicine on an empty stomach (no food or drink other than water for 1 hour before or 2 hours after dosing).  
Morning dose: take \_\_\_\_\_ mg (\_\_\_\_\_ capsules) AZD6244. \*\*\*\*\* Evening dose: take \_\_\_\_\_ mg (\_\_\_\_\_ capsules) AZD6244.
4. Record the date, the number of AZD6244 capsules you swallowed in the morning and again in the evening, and when you swallowed the medicine.
5. Record the daily dose onto the diary, including missed, skipped, or vomited doses. If you vomit after taking the tablets, the dose is replaced only if the tablets can actually be seen and counted. If you miss a dose, you should resume with the next scheduled dose.
6. If you have any comments or notice any side effects, please record them in the Comments column.
7. Please bring this form and your bottles of AZD6244 when you return for each appointment.

Day	Date	Time of morning dose	Dose taken	Time of evening dose	Dose taken	Comments

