## **5.7 Agent Administration**

Treatment will be administered on an outpatient basis. Reported adverse events and potential risks from the agents used in this protocol are described in Section [7](#). Appropriate dose modifications for these agents are described in Section [6](#). No investigational or commercial agents or therapies other than those described below may be administered with the intent to treat the patient's malignancy.

Patients in all treatment arms (Erlotinib, AZD6244, [MK2206](#), Lapatinib and Sunitinib) will be provided with a Medication Diary ([Appendix B](#)). They will be instructed in its use and asked to bring the diary with them to each appointment. A new copy of the Medication Diary will be given to patients whose dose is reduced due to adverse events. Patients should log in their daily dose onto the diary, including missed, skipped, or vomited doses. If the patient vomits after taking the tablets, the dose is replaced only if the tablets can actually be seen and counted. If a patient misses a dose, he or she should be instructed to resume dosing with the next scheduled dose.

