### 6.1.2 AZD6244 Hyd-Sulfate

**Table 8:** AZD6244 Monotherapy Dose Level Reductions

Dose Level	AZD6244 Dose
Starting Dose	75 mg BID
First Dose Reduction	50 mg BID
Second Dose Reduction	50 mg once daily

**Table 9:** Dosage Modification Criteria for AZD6244-related Toxicities

Event	AE Grade or Observation	Dose modification
Dermatology/Skin	Grade 1 or 2	Maintain dose
	Grade 3 or 4 or intolerable grade 2	Hold AZD6244 until < tolerable grade 2, then reduce 1 dose level and resume treatment  .
	Recurrent Grade 3	Hold AZD6244 until < tolerable grade 2, then reduce 1 additional dose level and resume treatment  .

	Recurrent Grade 3 after 2 dose reductions	Remove patient from study arm.
	Grade 4	Patients with grade 4 rash (i.e. life threatening generalized exfoliative ulceration; erythema multiforme/toxic epidermal necrolysis should be removed from study arm.
V  Diarrhea  (if anti-diarrheal treatment is ineffective)	Grade 1 or 2	Maintain dose; continue anti-diarrheal treatment. Loperamide (4 mg at first onset, followed by 2 mg every 2–4 hrs until diarrhea free for 12 hrs)
	Grade 3 or 4	Hold AZD6244 until < tolerable grade 2, loperamide; reduce 1 dose level and resume treatment  .
	Recurrent Grade 3 or 4	Hold AZD6244 until < tolerable grade 2, loperamide; reduce 1 additional dose level and resume treatment  .
	Recurrent Grade 3 or 4 after 2 dose reductions	Remove patient from study arm.
Hematologic  (neutrophils, platelets, hemoglobin)	Grade 1 or 2	Maintain dose
	Grade 3 or 4	Hold AZD6244 until < grade 2, then reduce 1 dose level and resume treatment.
	Recurrent Grade 3 or 4	Hold AZD6244 until < grade 2, then reduce 1 additional dose level and resume treatment.
	Recurrent Grade 3 or 4 after 2 dose reductions	Remove patient from study arm.
Liver Function  (serum bilirubin, AST, or ALT)	Grade 1 or 2	Maintain dose
	Grade 3 or 4	Hold AZD6244 until < grade 2, then reduce 1 dose level and resume treatment
	Recurrent Grade 3 or 4	Hold AZD6244 until < grade 2, then reduce 1 additional dose level and resume treatment
	Recurrent Grade 3 or 4 after 2 dose reductions	Remove patient from study arm.
Other non-	Grade 1 or 2	Maintain dose

hematological toxicity	Any Grade 2 of concern (e.g., prolonged cardiac, pulmonary, or neurotoxicity, intolerable stomatitis)	Hold AZD6244 until < grade 1, then reduce 1 dose level and resume treatment

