				# of capsule taken		
1						
2						
3						
4						

5						
6						
7						
8		V				
9						
10						
11						
12						
13						
14						
15			O			
16						
17						
18				T		
19					I	
20						
21						

Patient's signature \_\_\_\_\_

Physician's Office will complete this section:

1. Date patient started protocol \_\_\_\_\_
2. Date patient was removed from \_\_\_\_\_
3. Patient's planned total daily dose \_\_\_\_\_
4. Total number of capsules taken this month \_\_\_\_\_

D

*Abbreviated Title: Molecular Profiling NSCLC*

*Version Date: 01/07/2020*

5.	Physician/Nurse/Data Manager's Signature _____
----	--

V

O

I

D

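### The only AZD6244 patient diary prints a fixed twice-daily instruction, which contradicts the once-daily second dose reduction in Table 8

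*Combined protocol and SAP*

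**What the plan says.** Table 8 (Section 6.1.2, AZD6244) has three levels: 75 mg BID, then 50 mg BID, then "50 mg once daily". Only the last step changes the number of doses per day. Table 9 makes that level reachable, because a recurrent toxicity after the first reduction leads to one further reduction. It also has a row headed "Recurrent Grade 3 or 4 after 2 dose reductions", under which the patient leaves the study arm.

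Section 5.7 links the dosing table to the patient form: "A new copy of the Medication Diary will be given to patients whose dose is reduced due to adverse events".

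Appendix B contains one AZD6244 diary (Section 18.2.1). Item 3 states: "You will take AZD6244 by mouth twice each day about 12 hours apart". Two blanks for amounts follow, introduced by "Morning dose: take" and "Evening dose: take", each with space for milligrams and a capsule count. Item 4 asks the patient to "Record the date, the number of AZD6244 capsules you swallowed in the morning and again in the evening", and the daily log has matching morning and evening columns. The section that the office completes has a line for "Patient's planned total daily dose" but none for the number of doses per day.

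**The concern.** A patient who reaches the second reduction has already had toxicity recur at the first reduction. Under Section 5.7 that patient is handed a new diary whose printed frequency does not match the level in Table 8. The frequency is fixed text, and the form offers neither a once-daily version nor a field to change it.

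What is at stake is a dosing error in a patient being reduced for toxicity. If the printed frequency were followed with 50 mg per dose, the second reduction would not take effect. Table 9 might then count the patient as having had two reductions when the second was never taken.

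The form also affects the record. Unless the evening amount was completed as zero, an empty evening column at this level could mean either a once-daily schedule or missed doses.

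**Working it through.** The documents state no figure to reproduce. The check compares the passages and uses simple arithmetic.

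**Inputs**
- Dose levels: Table 8, Section 6.1.2 (AZD6244). The starting dose agrees with Section 5.7.1.2.
- Capsule strength: 25 mg (Section 9.1.2.5).
- Cycle length: 21 days (Section 5.3, and the 21 rows of the diary).
- Printed frequency: two doses per day (Section 18.2.1, item 3).

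**Formulas**
- Daily dose = mg per dose × doses per day.
- Capsules per day = daily dose ÷ 25.
- Capsules per cycle = capsules per day × 21.

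**Table 8 levels against the diary's printed frequency**

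| Level | Daily dose | Capsules per day | Capsules per cycle | Agrees with the diary? |
|---|---|---|---|---|
| Starting dose | 75 × 2 = 150 mg | 6 | 126 | Yes |
| First reduction | 50 × 2 = 100 mg | 4 | 84 | Yes |
| Second reduction | 50 × 1 = 50 mg | 2 | 42 | No |

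**Ways the form could be completed at the second reduction**
1. 50 mg in one blank and 0 in the other: 50 + 0 = 50 mg/day. This matches Table 8, and only the printed frequency is wrong.
2. 50 mg in both blanks, or 50 mg taken twice because the patient follows the printed frequency: 50 + 50 = 100 mg/day. The ratio to Table 8 is 100/50 = 2.0 (84/42 capsules per cycle), and the dose equals the first-reduction level.
3. 25 mg in both blanks: 25 + 25 = 50 mg/day. The total agrees with Table 8, but the schedule is one that Table 8 does not contain.

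**Comparison with the other arms**

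The erlotinib and lapatinib diaries print once-daily dosing, the sunitinib diary prints daily dosing with a drug holiday on days 29 to 42, and the MK-2206 diary prints weekly dosing. Each of these fits every level in its own reduction table (Tables 6, 12, 14 and 10). Only the AZD6244 table changes frequency between levels, and only its diary conflicts with it.

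**The case against.** The strongest reply is that the form prints no dose. Staff complete the morning and evening amounts separately and can enter zero for one of them, and they also record a planned total daily dose. Section 5.7 has patients instructed in the diary's use and asked to bring it to each appointment. The diary asks them to bring their bottles as well, and staff record the capsules taken and sign. These steps could reveal 84 capsules where 42 were expected, though only after the fact.

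This stands as far as it goes. A reader might infer that the diary itself instructs a patient to take double the Table 8 dose, and the documents do not support that. Doubling requires staff to enter 50 mg twice, or the patient to follow the printed frequency over the blanks. The reply does not remove the contradiction, however. The twice-daily wording stays printed above whatever amounts are entered, and the total-dose line states no frequency.

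The second reply is timing. Section 5.3 says the treatment arms stopped recruiting on 3/22/16. Sections 16.4 and 16.5 describe them as closed, with the study open only for molecular profiling. This also stands and limits the practical impact. The version dated 01/07/2020 nevertheless still carries both the dosing table and the diary.

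**Conclusion.** The contradiction is real and confined to one dose level: the diary's fixed frequency does not fit the second AZD6244 reduction in Table 8. The factor of 2.0 is conditional on 50 mg being entered or taken twice. The documents give no rate at which that would happen. With the arm closed, this is a form correction of limited present effect. It also matters for reading any second-reduction diaries already collected.

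Two further inferences are tempting but unsupported.

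- **A count of affected patients per stratum.** A reader might start from the 18/56 (32.1%) with treatment-related events of grade 3 or worse, reported for single-agent capsules in Appendix A. That figure pools dose cohorts from 25 to 100 mg BID. Such an event is not the same as a second reduction, and reaching the second reduction is not the same as being misdosed.
- **An effect on the rule of 5 responses in 20.** A reader might argue that early removal lowers the response count. Section 6 lets the investigator and the CTEP monitor keep a patient who would need a third reduction if there is evidence of benefit. Section 13.1.4.3 counts best response from the start of treatment, so an earlier confirmed response still counts. No effect on the rule can be shown from the documents.

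**What to change.** Reconcile Section 18.2.1 with Table 8 so that the diary's printed frequency matches the level prescribed. One way is to replace the fixed frequency in item 3 with a field that the site completes at each dispensing. Item 4, the log columns and the office section would be adjusted to agree, with a line for doses per day beside the total daily dose. Which dose or schedule is right is for the sponsor to settle, and nothing here favours either passage.

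The cost is one revised patient form. Design, sample size and analysis do not change. If any second-reduction diaries were collected, they should be read against the prescribed level before an empty dose column is counted as a missed dose.

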				# of capsule taken		
1						
2						
3						
4						

5						
6						
7						
8		V				
9						
10						
11						
12						
13						
14						
15			O			
16						
17						
18				T		
19					I	
20						
21						

Patient's signature \_\_\_\_\_

Physician's Office will complete this section:

1. Date patient started protocol \_\_\_\_\_
2. Date patient was removed from \_\_\_\_\_
3. Patient's planned total daily dose \_\_\_\_\_
4. Total number of capsules taken this month \_\_\_\_\_

D

*Abbreviated Title: Molecular Profiling NSCLC*

*Version Date: 01/07/2020*

5.	Physician/Nurse/Data Manager's Signature _____
----	--

V

O

I

D

## 18.2.2 MK-2206

## PATIENT'S MEDICATION DIARY

Today's date \_\_\_\_\_

Agent: MK-2206

Patient Name \_\_\_\_\_ (initials acceptable)  
ID \_\_\_\_\_

Patient Study

## INSTRUCTIONS TO THE PATIENT:

1. Complete one form for each cycle of treatment.
2. You will take MK-2206 tablets by mouth once every week. You should take the tablets 2 hours before or after a meal.
3. Dose: take \_\_\_\_\_ 5 mg tablet(s), \_\_\_\_\_ 25 mg tablet(s), and/or \_\_\_\_\_ 200 mg tablet(s) once every week.
4. Record the date, the number of tablets of each size of tablet that you took, and when you took them.
5. Record the daily dose onto the diary, including missed, skipped, or vomited doses. If you vomit after taking the tablets, the dose is replaced only if the tablets can actually be seen and counted. If you miss a dose, you should resume with the next scheduled dose.
6. If you have any comments or notice any side effects, please record them in the Comments column.
7. Please bring this form and your bottles of MK-2206 tablets when you return for each appointment.

Day	Date	Time of dose	# of tablets taken			Comments
			5 mg	25 mg	200 mg	
1						
2-7						Days 2-7 drug holiday
8						
9-14						Days 9-14 drug holiday
15						
16-21						Days 16-21 drug holiday
22						
23-28						Days 23-28 drug holiday

Patient's signature

Physician's Office will complete this section:

1. Date patient started protocol treatment \_\_\_\_\_
2. Date patient was removed from study \_\_\_\_\_
3. Patient's planned total daily dose \_\_\_\_\_
4. Total number of tablets taken this month \_\_\_\_\_
5. Physician/Nurse/Data Manager's Signature \_\_\_\_\_

O

I

D

### 18.2.3 Sunitinib

#### PATIENT'S MEDICATION DIARY

Today's date \_\_\_\_\_

Agent: Sunitinib

Patient Name \_\_\_\_\_ (initials acceptable) Patient Study ID \_\_\_\_\_

#### INSTRUCTIONS TO THE PATIENT:

1. Complete one form for each 4 week-period while you take sunitinib.
2. You will take your dose of sunitinib by mouth each day in the morning. You will take \_\_\_\_ 12.5 mg capsule(s), and/or \_\_\_\_ 25 mg capsule(s); or \_\_\_\_ 50 mg capsule. You may take the capsules with or without food as you wish.
3. Record the date, the number of capsules of each size you took, and when you took them.
4. Record the daily dose onto the diary, including missed, skipped, or vomited doses. If you vomit after taking the tablets, the dose is replaced only if the tablets can actually be seen and counted. If you miss a dose, you should resume with the next scheduled dose.
5. If you have any comments or notice any side effects, please record them in the Comments column.
6. Wash your hands with soap and water after touching the capsule(s). Do not share this medication with anyone.
7. Please return unused sunitinib capsules (or empty bottles) and this form to your physician when you go for your next appointment.

Day	Date	Time of daily dose	# of capsules taken			Comments
			12.5 mg	25 mg	50 mg	
1						
2						
3						
4						
5						
6						
7						
8						

9						
10						
11						
12	V					
13						
14						
15						
16						
17						
18			O			
19						
20						
21						
22					T	
23						
24					I	
25						
26						
27						D
28						
29-42						Days 29-42 drug holiday

Patient's signature \_\_\_\_\_

**Abbreviated Title: Molecular Profiling NSCLC**

**Version Date: 01/07/2020**

Physician's Office will complete this section:

1. Date patient started protocol treatment \_\_\_\_\_
2. Date patient was removed from study \_\_\_\_\_
3. Patient's planned total daily dose \_\_\_\_\_
4. ~~Total~~ number of tablets taken this month \_\_\_\_\_
5. Physician/Nurse/Data Manager's Signature \_\_\_\_\_

V

O

I

D

#### 18.2.4 Erlotinib

#### PATIENT'S MEDICATION DIARY

Today's date \_\_\_\_\_

[figure not shown]
[figure not shown]
Agent: Erlotinib

Patient Name \_\_\_\_\_ (initials acceptable) Patient Study ID \_\_\_\_\_

#### INSTRUCTIONS TO THE PATIENT:

[figure not shown]
[figure not shown]
[figure not shown]
1. Complete one form for each cycle of treatment.
2. You will take the Erlotinib tablets by mouth once every day. You will take \_\_\_\_ 25mg tablets, \_\_\_\_ 100mg tablet, \_\_\_\_ 150mg tablet. You should take the tablets either 1 hour before or two hours after a meal. Take the tablets with 8 ounces of water.
3. Record the date, the number of tablets of each size of tablet that you took, and when you took them.
4. Record the daily dose onto the diary, including missed, skipped, or vomited doses. If you vomit after taking the tablets, the dose is replaced only if the tablets can actually be seen and counted. If you miss a dose, you should resume with the next scheduled dose.
5. If you have any comments or notice any side effects, please record them in the Comments column.
6. Please bring this form and your bottles of Erlotinib tablets when you return for each appointment.

Day	Date	Time of dose	# of tablets taken			Comments
			mg	mg	mg	
1						
2						
3						
4						
5						
6						
7						
8						
9						

10						
11						
12						
13						
14						
15						
16						
17						
18						
19						
20						
21						

Patient's signature

Physician's Office will complete this section:

1. Date patient started protocol treatment 
2. Date patient was removed from study 
3. Patient's planned total daily dose 
4. Total number of tablets taken this month 
5. Physician/Nurse/Data Manager's Signature 

18.2.5 Lapatinib

CTEP-assigned Protocol # \_\_\_\_\_

PATIENT'S MEDICATION DIARY

Today's date \_\_\_\_\_

[figure not shown]
[figure not shown]
Agent: Lapatinib

Patient Name \_\_\_\_\_ (initials acceptable) Patient Study ID \_\_\_\_\_

INSTRUCTIONS TO THE PATIENT:

[figure not shown]
[figure not shown]
[figure not shown]
[figure not shown]
1. Complete one form for each cycle of treatment.
2. You will take Lapatinib tablets by mouth once every day. You should take the tablets 1 hours before or after a meal  
Dose: take \_\_\_ mg tablets.
3. Record the date, the number of tablets of each size of tablet that you took, and when you took them.
4. Record the daily dose onto the diary, including missed, skipped, or vomited doses. If you vomit after taking the tablets, the dose is replaced only if the tablets can actually be seen and counted. If you miss a dose, you should resume with the next scheduled dose.
5. If you have any comments or notice any side effects, please record them in the Comments column.
6. Please bring this form and your bottles of Lapatinib tablets when you return for each appointment.

Day	Date	Time of dose	# of tablets taken			Comments
			mg	N/A	N/A	
1						
2						
3						
4						
5						
6						
7						
8						
9						
10						

11						
12						
13						
14						
15						
16						
17						
18						
19						
20						
21						

Patient's signature

Physician's Office will complete this section:

1. Date patient started protocol treatment 
2. Date patient was removed from study 
3. Patient's planned total daily dose 
4. Total number of tablets taken this month 
5. Physician/Nurse/Data Manager's Signature 

### 18.3 Appendix C: Performance Status Criteria

ECOG Performance Status Scale		Karnofsky Performance Scale	
Grade	Descriptions	Percent	Description
0	Normal activity. Fully active, able to carry on all pre-disease performance without restriction.	100	Normal, no complaints, no evidence of disease.
		90	Able to carry on normal activity; minor signs or symptoms of disease.
1	Symptoms, but ambulatory. Restricted in physically strenuous activity, but ambulatory and able to carry out work of a light or sedentary nature (e.g., light housework, office work).	80	Normal activity with effort; some signs or symptoms of disease.
		70	Cares for self, unable to carry on normal activity or to do active work.
2	In bed <50% of the time. Ambulatory and capable of all self-care, but unable to carry out any work activities. Up and about more than 50% of waking hours.	60	Requires occasional assistance, but is able to care for most of his/her needs.
		50	Requires considerable assistance and frequent medical care.
3	In bed >50% of the time. Capable of only limited self-care, confined to bed or chair more than 50% of waking hours.	40	Disabled, requires special care and assistance.
		30	Severely disabled, hospitalization indicated. Death not imminent.
4	100% bedridden. Completely disabled. Cannot carry on any self-care. Totally confined to bed or chair.	20	Very sick, hospitalization indicated. Death not imminent.
		10	Moribund, fatal processes progressing rapidly.
5	Dead.	0	Dead.

#### 18.4 Appendix D: New York Heart Association Classifications

Clinical Evaluation of Functional Capacity of Patients with Heart Disease in Relation to Ordinary Physical Activity

Class	Cardiac Symptoms	Limitations	Need for Additional Rest*	Physical Ability to work**
I	None	None	None	Full time
II	Only moderate	Slight	Usually only slight or occasional	Usually full time
III	Defined, with less than ordinary activity	Marked	Usually moderate	Usually part time
IV	May be present even at rest, and any activity increases discomfort	Extreme	Marked	Unable to work

\* To control or relieve symptoms, as determined by the patient, rather than as advised by the physician.

\*\* At accustomed occupation or usual tasks.

Reference: Bruce, R. A.: Mod. Concepts Cardiovasc. Dis. 25:321, 1956.

(Modified from New York Heart Association, 1953).

